#### **4.4. Randomization**

Women will only be randomized once the decision is made to do a cesarean. A confidential web-based randomization sequence will be prepared by using blocks of variable sizes, stratified by study site, BMI category (30-39.9 and  $\geq 40$  kg/m^2) and scheduled/non-labor versus unscheduled/labor cesareans. The randomization sequence will be maintained centrally by the study statistician. The patient's group assignment will be revealed once basic information including confirmation of the inclusion criteria are submitted online.

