##### *Preoperative care*

Routine preoperative cesarean care at each center will be given to patients by their clinical providers. These procedures are similar and all study sites have agreed on basic standardization of SSIs prevention strategies as well as diagnosis and treatment (**Table 2**).

Standardized preoperative procedures include:

- Clipping of hair at site of incision immediately prior cesarean as needed
- Preoperative antibiotics within 60 minutes prior to incision. Typical preoperative antibiotic used is 2-3 g of cefazolin. Penicillin-allergic patients will receive gentamicin and clindamycin. Patients with chorioamnionitis will receive ampicillin, gentamicin, and clindamycin.
- Skin preparation with chlorhexidine-alcohol or povidone-iodine solution with 3-minutes of drying time prior to draping.
- Adherence to these procedures will be recorded and monitored.

*Intraoperative care*

- Choice of incision will be left to the surgeon. The typical incision for a cesarean is a Pfannenstiel (low transverse) skin incision, although body habitus (particularly in obese women) and prior surgeries may dictate the use of a high transverse skin incision above the pannus or a vertical midline skin incision
- The preferred uterine incision will be low transverse, unless intraoperative findings such as dense adhesions or poorly developed lower uterine segment necessitate a classical or high transverse incision
- Closure of the subcutaneous layer if  $\geq 2$  cm
- The preferred skin closure at the participating centers is subcuticular suture. However, type of incision, scar tissue, and patient preference may play a role in the decision to use staples

**Table 2:** Routine infection prevention practices at each study site

	Washington University in St. Louis	University of Alabama at Birmingham	Ochsner Medical Center	Mercy Hospital in St. Louis	Indiana University
Hair clipping	Clipping immediate preop if needed	Clipping immediate preop if needed	Clipping immediate preop if needed	Clipping immediate preop if needed	Clipping immediate preop if needed
Skin Prep	Chlorhexidine-alcohol; iodine-alcohol if allergic to chlorhexidine	Povidone-iodine + Chlorhexidine-alcohol; chlorhexidine gluconate alone for urgent cases	Chlorhexidine for non-urgent cases; betadine for urgent	Betadine-alcohol, chlorhexidine-alcohol for betadine allergy	Chlorhexidine-alcohol for non-urgent cases; betadine for urgent

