### **5.3. Data Processing**

The Data Management Center (DMC) at Washington University School of Medicine will be responsible for data management and analysis in accordance with the analysis plan to be finalized by the steering committee and approved by the DSMB. The Data Management Team based at Washington University includes an experienced statistician and a database manager. Each site PI and nurse coordinator will be responsible for liaison with the DMC including transmitting de-identified abstracted information contained in the data collection forms. Data management at each site will include: procedures for data entry, data editing, and compilation; procedures for data transmittal; and procedures for quality control, data verification, confidentiality and security. Data will be collected and managed with REDCap (Research Electronic Data Capture), an established, secure, web-based data capture and management tool developed at Vanderbilt University and supported by the bioinformatics team at WUSM (<http://www.biostat.wustl.edu/redcap/>). The security of the database will be maintained by the use of dedicated password protected encrypted computers with multiple private backups (daily, weekly, and monthly including on- and off-site storage for protection against disaster).

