## **6.2. Data Analysis Plan**

### **6.2.1. Primary Analyses**

Data analyses will adhere closely to the CONSORT guidelines. Analyses will follow the intention-to-treat principle in which subjects will be analyzed in the group to which they were randomized, regardless of whether or not they received the assigned intervention.

Descriptive statistics will characterize the group of individuals recruited and investigate comparability of the two groups at baseline. Formal statistical testing will be limited to selected baseline characteristics considered to be prognostic factors for the primary outcome such as emergent cesarean, type of skin incision, and prolonged rupture of membranes. The categorical prognostic factors will be compared between trial groups by using the Chi-squared or Fisher's exact tests as appropriate. The two-group independent t-test and Mann-Whitney U test will be used to compare normal and non-normally distributed continuous variables, respectively. The primary outcome and other categorical secondary outcomes will be compared between intervention groups by using the Cochran-Mantel-Haenszel test. We will calculate common relative risks and 95% confidence intervals associated with the primary and secondary outcomes.

We will use the Breslow-Day test to assess homogeneity of the effect across subgroups (study sites, BMI category [30 – 39.9,  $\geq 40$ ], and scheduled/non-labor or unscheduled/labor cesareans, skin incision type [low transverse, high transverse, midline vertical], diabetes status). We will also conduct time-to-event analyses by using Kaplan Meier and Cox regression models to examine the pattern of SSIs in the two groups.

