### **6.2.2. Secondary Analyses**

#### *Adjusted estimates*

We will perform analyses aimed at obtaining estimates of treatment effectiveness, adjusting for any imbalances in baseline subject characteristics between groups. The objectives of these analyses are to estimate the influence of covariates on the outcome and to use them to improve the estimated difference between treatment groups. Logistic regression models will be used to identify and estimate the effect of multiple prognostic factors on the probability of SSI and other categorical outcomes.

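### Skin-incision type is treated as a baseline variable although the surgeon chooses it after randomization, and the adjusted analysis lets observed imbalances pick its covariates

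*Combined protocol and SAP*

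**What the plan says.** Section 6.2.1 restricts formal between-group testing to a few factors, described as "selected baseline characteristics considered to be prognostic factors for the primary outcome such as emergent cesarean, type of skin incision"; the third example given is a long interval since the membranes ruptured. It also lists "skin incision type [low transverse, high transverse, midline vertical" among the subgroups for the Breslow-Day test, beside site, BMI category, labor status and diabetes.

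The timing comes from Section 4. Enrollment precedes the cesarean (4.3). Randomization follows the decision to operate, is "stratified by study site, BMI category" and labor status, and the "group assignment will be revealed once basic information including confirmation of the inclusion criteria are submitted online" (4.4). Under Intraoperative care in 4.5, "Choice of incision will be left to the surgeon".

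Section 6.2.2 describes secondary analyses "adjusting for any imbalances in baseline subject characteristics between groups". One of its two stated objectives is to estimate how covariates influence the outcome; the other is "to use them to improve the estimated difference between treatment groups". No covariate list, threshold or measure of imbalance is given. Section 5.3 says that analysis will be "in accordance with the analysis plan to be finalized by the steering committee and approved by the DSMB".

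**The concern.** There are two linked problems, both confined to analyses outside the primary comparison.

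**Incision type.** A variable fixed after randomization cannot serve as a check on randomization, because a difference between arms need not be chance. If it enters a treatment-effect model or defines a subgroup, the resulting contrast is no longer protected by randomization. The baseline label in 6.2.1 invites both uses.

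**The imbalance rule.** When observed differences select covariates, the adjusted model is not known until the arms have been compared, and an undefined imbalance leaves room for choice. The rule also selects on the wrong property. Adjustment gains precision from factors that predict infection, whether or not they are imbalanced. The factors on which the trial stratified are those least likely to look imbalanced, so the rule tends to leave them out.

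At stake is the credibility of the adjusted estimate and of the incision subgroup.

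**Working it through.** **1. Timing.** The sequence is enrollment before cesarean (4.3), randomization once cesarean is decided, with the assignment shown after online submission (4.4), then the incision during the operation (4.5). The schedule of events marks randomization in the enrollment column only. No single sentence says that incision follows randomization, but the sections together allow no other natural reading. No record of a planned incision before allocation is described.

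**2. The plan's own figure.** Section 6.1.1 gives 10% versus 7%, two-sided 5%, 80% power and 5% loss. With pooled variance and no continuity correction:

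n per arm = [1.96·√(2·0.085·0.915) + 0.8416·√(0.10·0.90 + 0.07·0.93)]² / 0.03² = 1356, or 2712 in total.

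Allowing for loss gives 2712/0.95 = 2855 or 2712·1.05 = 2848, so the stated 2850 reproduces. It is not in dispute. The steps below use 1425·0.95 = 1353.75 women per arm.

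**3. How far one imbalanced covariate moves the estimate.** Assumed: a binary factor with prevalence q of 10–50% and relative risk R for infection of 1.5–2, whose imbalance d just reaches P = 0.05.

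- d = 1.96·√(2q(1−q)/1353.75): 2.3 points at q = 0.1 and 3.8 points at q = 0.5.
- Factor on the treatment RR = [1 + (q + d/2)(R − 1)] / [1 + (q − d/2)(R − 1)], which runs from 1.011 to 1.027.
- At the upper end, 0.70/1.027 = 0.68 and 0.70·1.027 = 0.72.

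**4. How often the cutoff matters.** If imbalance meant P < 0.05 on independent tests, the chance of at least one chance flag is 1 − 0.95^k: 14.3% for 3 factors, 22.6% for 5 and 40.1% for 10. In 1,500 simulated trials (1354 per arm, five independent factors, each with prevalence 30% and odds ratio 2, logistic model), selecting at P < 0.05 or at P < 0.20 gave different significance verdicts on the adjusted effect in 2.7% (Monte Carlo SE 0.4 points). A separate run of 600 trials gave 1.7% (SE about 0.5). I read this as about 2–3%. In a further simulation, also on assumed inputs, a fixed list gave power of about 85% against 83–84% for the imbalance rule. The gain of 1 to 2 points is the informative part, since the level depends on the inputs.

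**5. Incision, as a what-if only.** Assumed: 10% of women have an incision other than low transverse, with twice the infection risk, and a share s of all women, from the lower-risk group, is moved into that category in one arm.

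- Control risks: 0.10/1.1 = 9.09% and 18.18%.
- Dilution factor on the subgroup risk: [(0.10·0.1818 + s·0.0909)/(0.10 + s)]/0.1818 = 0.917 at s = 0.02.
- Subgroup RR: 0.70·0.917 = 0.64 if the NPWT arm shifts, or 0.70/0.917 = 0.76 if the control arm does.
- Mantel-Haenszel RR stratified on incision: 0.689 or 0.712. The unstratified intention-to-treat RR stays at 0.700.
- Precision: about 135 women per arm in the subgroup, with 24.6 and 17.2 events. SE(log RR) = √(1/17.2 − 1/135.4 + 1/24.6 − 1/135.4) = 0.290, so the 95% CI is about 0.40–1.23.

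The distortion sits well inside the subgroup's own uncertainty. At s = 0 there is none.

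**The case against.** The strongest reply is that little depends on this. The adjusted estimates and subgroups do not drive the primary conclusion. Incision type is called baseline only as an example in one sentence, while 4.5 files it under intraoperative care and sends operative variation to secondary analyses. Nothing says that the factors tested in 6.2.1 feed the model in 6.2.2, so the route from the label to the adjusted model is inferred. Estimating the influence of covariates is a legitimate objective, and incision type is a proper subject for it. The final analysis plan may yet supply a covariate list.

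Most of this stands, and it limits the point to a minor one. It does not make incision type a baseline variable. Nor is the second half only a request for detail, because 6.2.2 does state a rule, and a fixed list is a better one.

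A reader might infer that surgeons who know the arm choose incisions accordingly and so bias the results. The documents do not support that. Section 4.4 does not say to whom the assignment is shown, and no section says that the surgeon knows it at incision. The reasons that 4.5 gives for unusual incisions, body habitus and prior surgeries, exist before randomization. Step 5 is also simplified: it uses two incision groups where 6.2.1 names three, and assumes that incision separates risk groups perfectly. A different causal assumption, in which the shift itself alters infection risk, makes adjustment move the estimate the other way. It shows scale, not a predicted bias.

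**Conclusion.** The point holds as a minor one. Skin-incision type is mislabelled as a baseline characteristic, and the imbalance rule in 6.2.2 chooses covariates from the data while tending to omit the stratification factors. On assumed prevalence and risk, an RR of 0.70 would move to about 0.68–0.72, and about 2–3% of significance verdicts on the adjusted effect would depend on the cutoff. Only the sample size, event rates and loss come from the plan; the other inputs are assumptions.

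A reader might go further and doubt the primary result. That is not supported: the intention-to-treat Cochran-Mantel-Haenszel comparison uses neither incision type nor the imbalance-selected covariates, as far as the plan states, and the sample size is unaffected. The confidence here is in the timing and in the rule, not in any demonstrated bias.

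**What to change.** 1. In 6.2.1, move skin-incision type out of the baseline characteristics to be tested and report it by arm as an intraoperative variable. Keep it out of the adjusted treatment-effect model, and label its subgroup analysis post-allocation and exploratory. It may still be studied as a risk factor for infection.
2. In 6.2.2, and in the analysis plan that 5.3 leaves to be finalized, replace the imbalance rule with a fixed list of pre-randomization covariates, set before the first interim analysis (7.3): site, BMI category, scheduled/labor status and diabetes, plus emergent cesarean and prolonged rupture of membranes where their status at randomization is recorded.

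The cost is mainly wording. The sample size and the release of assignments do not change. The plan does not say whether status at randomization is recorded for the last two covariates, so that must be checked before they are listed. The downside is that a factor outside the list may be imbalanced by chance; adjustment for it can be shown as a labelled sensitivity analysis.

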#### **4.8.2. Secondary Outcomes**

[figure not shown]
- Individual components of the primary outcome (superficial or deep SSI)
- Organ space SSI (endometritis)
- Other individual wound complications: dehiscence  $\geq 2$  cm, hematoma, seroma, erythema

- Composite of any wound complications
- Patient pain and satisfaction scores at discharge and postoperative day 30
- Patient satisfaction with aesthetic appearance (scale of 0 - 10) at postoperative day 30
- Healthcare resource utilization: physician office or ED visits, antibiotics for SSI, hospital readmission for SSIs, home health for SSI, wound clinic for SSI
- Adverse events: skin blistering, allergic reaction, wound bleeding

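### The only test named for continuous data ignores the randomization strata, and no sentence clearly gives an analysis for the pain, satisfaction and appearance scores

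*Combined protocol and SAP*

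**What the plan says.** All references are to the combined protocol and SAP.

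- **Outcomes.** Section 4.8.2 lists "Patient pain and satisfaction scores at discharge and postoperative day 30" among the secondary outcomes, together with a 0–10 rating of satisfaction with appearance at day 30.
- **Randomization.** Section 4.4: "A confidential web-based randomization sequence will be prepared by using blocks of variable sizes, stratified by study site, BMI category". The sentence goes on to add a third factor, scheduled/non-labor against unscheduled/labor cesarean.
- **Tests.** The relevant paragraph of Section 6.2.1 opens with the comparability of the groups at baseline and restricts formal testing to selected prognostic factors. It continues: "The categorical prognostic factors will be compared between trial groups by using the Chi-squared or Fisher's exact tests as appropriate". Next comes the sentence on continuous data: "The two-group independent t-test and Mann-Whitney U test will be used to compare normal and non-normally distributed continuous variables, respectively". Only then does it turn to outcomes: "The primary outcome and other categorical secondary outcomes will be compared between intervention groups by using the Cochran-Mantel-Haenszel test", followed by "We will calculate common relative risks and 95% confidence intervals associated with the primary and secondary outcomes".
- **Adjusted analyses.** Section 6.2.2, under *Adjusted estimates*, promises treatment estimates "adjusting for any imbalances in baseline subject characteristics between groups". One stated aim for the covariates is "to use them to improve the estimated difference between treatment groups". The only model named there is logistic regression, for SSI and other categorical outcomes.

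**The concern.** The categorical outcomes have a stratified test and a matching effect measure. The score outcomes have neither: a relative risk does not apply to a 0–10 score, and the Cochran-Mantel-Haenszel sentence is limited to categorical outcomes. The one sentence that could cover the scores names two tests that take no account of the strata.

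Stratified randomization balances the arms on site, BMI category and labor status. If those factors predict the score, the estimated difference varies less than an unstratified standard error supposes. Intervals come out wider than they need be, and some power is lost. The Mann-Whitney branch, as written, also comes with no stated estimate or interval, and bounded scores may well be skewed enough to end up there. At stake are the precision and clarity of the patient-reported secondary results.

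**Working it through.** **1. Which sentence covers the scores?** Outside the economic analysis, which handles costs and QALYs separately, there are three candidates.

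- The t-test/Mann-Whitney sentence follows the tests for categorical baseline factors and says *variables*, not outcomes. It reads most naturally as their continuous counterpart, but it does not exclude outcomes.
- The Cochran-Mantel-Haenszel and relative-risk sentences concern outcomes but do not fit scores.
- *Adjusted estimates* in Section 6.2.2 is triggered by imbalance. The stratification factors are balanced by design, so that trigger would not normally select them, and no model for a continuous outcome is named.

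So the scores are either analysed without the strata or have no stated analysis.

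**2. The plan's own figure.** No sample-size figure is given for the scores. The total of 2850 in Section 6.1.1 is for SSI at 10% against 7%, 80% power, two-sided 5%. With pooled variance and no continuity correction:

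n per arm = [1.960·√(2·0.085·0.915) + 0.842·√(0.10·0.90 + 0.07·0.93)]² / 0.03² = 1356, or 2712 in total.

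Allowing for 5% loss gives 2712/0.95 = 2855, or 2712 × 1.05 = 2848. The 2850 reproduces.

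**3. Size of the effect on the scores.** Inputs:

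- Evaluable women per arm: 2850 × 0.95 / 2 ≈ 1353, applying the plan's 5% loss to the scores.
- R², the share of within-arm score variance explained by the strata: not in the documents; 1–10% is assumed.
- SD of the scores: not in the documents, so differences are in SD units.

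Formulas:

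- Difference detectable with 80% power, unadjusted: (1.960 + 0.842)·√(2/1353) = 0.108 SD.
- Adjusted: the same × √(1 − R²). The standard error shrinks by the same factor.
- Extra women the unadjusted test needs for equal precision: 1/(1 − R²) − 1.
- Adjusted power at 0.108 SD: Φ(2.802/√(1 − R²) − 1.960).
- Actual two-sided type I error of the unadjusted test: 2·[1 − Φ(1.960/√(1 − R²))].

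| Assumed R² | SE reduction | Extra women needed unadjusted | Detectable difference, adjusted | Power at 0.108 SD, adjusted | Type I error, unadjusted test |
|---|---|---|---|---|---|
| 1% | 0.5% | 1.0% | 0.107 SD | 80.4% | 4.9% |
| 5% | 2.5% | 5.3% | 0.105 SD | 82.0% | 4.4% |
| 10% | 5.1% | 11.1% | 0.102 SD | 84.0% | 3.9% |

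The gain is 0.4 to 4 percentage points of power. The detectable difference is between 0.10 and 0.11 SD with or without adjustment.

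**The case against.** The strongest objection is that the plan does not say the scores will be compared by these tests. A reader might infer a firm commitment to them, but the sentence sits among baseline comparisons and names no outcome. That stands, and it is why the point is one of unclear specification. It does not remove the point, because the other reading leaves listed outcomes with no stated method.

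Second, Section 6.2.2 plans adjusted estimates that use covariates to improve the estimated difference. The intention is there. The trigger and the named model do not reach the scores.

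Third, a reader might infer that no effect size would be available. That goes too far: a t-test yields a mean difference with a confidence interval, and a Mann-Whitney test can be accompanied by a shift estimate. What is missing is an adjusted estimate, and a stated one.

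Fourth, a reader might expect a much larger loss, because Table 2 shows the standard dressing differing by site (honeycomb at two sites, abdominal pressure dressing at three). The documents do not support that.

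- Only the control arm's dressing differs by site. Suppose control-arm site means have variance V, the NPWT arm has none, and within-site variance W is equal in both arms. The site main effect then has variance V/4, and total within-arm variance averages W + V/2. For R² = (V/4)/(W + V/2) to reach 5%, 10% or 20%, site must explain about 18%, 33% or 57% of control-arm variance. The last is not plausible from this mechanism, and even 10% is generous.
- Those dressings are listed for 24–48 hours. The documents give no reason why they should drive day-30 pain or appearance.

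Finally, adjusting secondary scores is good practice, and its absence is not an error. That also stands, and it limits the weight of the point.

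**Conclusion.** The point holds as a minor improvement. The plan's only named method for continuous variables is unstratified, it is unclear whether that method is meant for outcomes, and nothing else covers the pain, satisfaction and appearance scores. If it is used for them, the standard error is larger than it need be by an amount the documents cannot fix. Over an assumed R² of 1–10%, adjustment would reduce it by about 0.5–5%.

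A reader might infer that results would be biased or that the main conclusions are at risk. Neither follows. The unadjusted comparison after stratified randomization is unbiased and errs on the conservative side. The primary SSI analysis, the adverse-event comparison and the cost-effectiveness analysis do not depend on it. The figures rest on the assumed R², the plan's 5% loss applied to the scores, well-balanced strata and the normal approximation.

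**What to change.** In Section 6.2.1, separate the baseline comparisons from the outcome analyses and name the score outcomes. For each pain, satisfaction and appearance score, specify linear regression on arm with site, BMI category and scheduled/unscheduled status as covariates and robust standard errors. Report the adjusted mean difference with its 95% confidence interval. A van Elteren test stratified by the same factors may be added as a rank-based sensitivity analysis; it supplies a p-value and no estimate, so it should not replace the regression.

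The cost is wording only. The three factors are already recorded for randomization. With the five sites in Table 2 they add 4 + 1 + 1 = 6 covariates, against roughly 2700 evaluable women (2 × 1353 = 2706). Fixing the model in advance also removes a choice between two tests that would depend on the observed distribution. Section 5.3 leaves the analysis plan to be finalized by the steering committee and approved by the DSMB, so the change can be made there.
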